1.3 Schedule of Activities (SoA)

Study Period	Screening	Intervention										Follow-up		Comments
		1	2	Phone Contact	3	Phone Contact	4	Phone Contact	5	Phone Contact	6	Phone Contact	7	
Visit Number:	1	2	Phone Contact	3	Phone Contact	4	Phone Contact	5	Phone Contact	6	Phone Contact	7	Phone Contact ^d	Results from all screening procedures at Visit 1 must be available before randomization into the study at Visit 2 (Day 1), which must occur ≤30 days after Visit 1.
Scheduled Time:		Day 1	Day 15	Day 30	Day 45	Day 60	Day 75	Day 90	9 Months after Allo-HSCT	12 Months after Allo-HSCT	15 days after Visit 6	30 Days after Visit 6	6 Months after Visit 6	
Visit Window:	Within 30 days before Visit 2	90 to 180 days after Allo-HSCT	Day 15 to Day 19 after Visit 2 ^a	Day 30 to Day 44 after Visit 2 ^a	Day 15 to Day 19 after Visit 3 ^b	Day 30 to Day 44 after Visit 3 ^b	Day 15 to Day 19 after Visit 4 ^c	Day 30 to Day 44 after Visit 4 ^c	Day 256 to Day 284 after Allo-HSCT	Day 335 to Day 395 after Allo-HSCT	Day 15 to Day 19 after Visit 6	Day 30 to Day 44 after Visit 6	Day 166 to Day 194 after Visit 6 ^d	
Administrative and General Procedures														
Informed Consent	X													Consent must be obtained before any study procedures.
Informed Consent for Future Biomedical Research (Optional)	X													Consent for future biomedical research samples must be obtained before the blood sample for ≥18 years of age and saliva for <18 years of age (DNA sample) is collected.
Assignment of Screening Number	X													
Inclusion/Exclusion Criteria	X	X												
Medical History	X	X												The participant's medical history for the 5 years prior to these visits will be reviewed. History of tobacco use will also be collected for all participants.

Study Period	Screening	Intervention										Follow-up		Comments
		1	2	Phone Contact	3	Phone Contact	4	Phone Contact	5	Phone Contact	6	Phone Contact	7	
Visit Number:	1	2	Phone Contact	3	Phone Contact	4	Phone Contact	5	Phone Contact	6	Phone Contact	7	Phone Contact ^d	Results from all screening procedures at Visit 1 must be available before randomization into the study at Visit 2 (Day 1), which must occur ≤30 days after Visit 1.
Scheduled Time:		Day 1	Day 15	Day 30	Day 45	Day 60	Day 75	Day 90	9 Months after Allo-HSCT	12 Months after Allo-HSCT	15 days after Visit 6	30 Days after Visit 6	6 Months after Visit 6	

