Visit Window:	Within 30 days before Visit 2	90 to 180 days after Allo-HSCT	Day 15 to Day 19 after Visit 2 ^a	Day 30 to Day 44 after Visit 2 ^a	Day 15 to Day 19 after Visit 3 ^b	Day 30 to Day 44 after Visit 3 ^b	Day 15 to Day 19 after Visit 4 ^c	Day 30 to Day 44 after Visit 4 ^c	Day 256 to Day 284 after Allo-HSCT	Day 335 to Day 395 after Allo-HSCT	Day 15 to Day 19 after Visit 6	Day 30 to Day 44 after Visit 6	Day 166 to Day 194 after Visit 6 ^d	
Screening Laboratory Tests	X													Complete blood count with differential, blood chemistry (including renal function).
Assignment of Randomization Number		X												
Participant Identification Card	X													
Prior/Concomitant Medication and Non-Study Vaccination Review		X	X	X	X	X	X	X		X	X	X		
V114 or Prevnar 13™ Administration (Blinded)		X		X		X								At each of the identified visits, participants will receive either a single dose of V114 or a single dose of Prevnar 13™.

Study Period	Screening	Intervention										Follow-up		Comments
Visit Number:	1	2	Phone Contact	3	Phone Contact	4	Phone Contact	5	Phone Contact	6	Phone Contact	7	Phone Contact ^d	
Scheduled Time:		Day 1	Day 15	Day 30	Day 45	Day 60	Day 75	Day 90	9 Months after Allo-HSCT	12 Months after Allo-HSCT	15 days after Visit 6	30 Days after Visit 6	6 Months after Visit 6	Results from all screening procedures at Visit 1 must be available before randomization into the study at Visit 2 (Day 1), which must occur ≤30 days after Visit 1.
Visit Window:	Within 30 days before Visit 2	90 to 180 days after Allo-HSCT	Day 15 to Day 19 after Visit 2 ^a	Day 30 to Day 44 after Visit 2 ^a	Day 15 to Day 19 after Visit 3 ^b	Day 30 to Day 44 after Visit 3 ^b	Day 15 to Day 19 after Visit 4 ^c	Day 30 to Day 44 after Visit 4 ^c	Day 256 to Day 284 after Allo-HSCT	Day 335 to Day 395 after Allo-HSCT	Day 15 to Day 19 after Visit 6	Day 30 to Day 44 after Visit 6	Day 166 to Day 194 after Visit 6 ^d	
PNEUMOVAX™23 Administration or V114 or Prevnar 13™ Administration (Blinded)										X				

Study Period	Screening	Intervention										Follow-up		Comments
Visit Number:	1	2	Phone Contact	3	Phone Contact	4	Phone Contact	5	Phone Contact	6	Phone Contact	7	Phone Contact ^d	

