Visit Window:	Within 30 days before Visit 2	90 to 180 days after Allo-HSCT	Day 15 to Day 19 after Visit 2 ^a	Day 30 to Day 44 after Visit 2 ^a	Day 15 to Day 19 after Visit 3 ^b	Day 30 to Day 44 after Visit 3 ^b	Day 15 to Day 19 after Visit 4 ^c	Day 30 to Day 44 after Visit 4 ^c	Day 256 to Day 284 after Allo-HSCT	Day 335 to Day 395 after Allo-HSCT	Day 15 to Day 19 after Visit 6	Day 30 to Day 44 after Visit 6	Day 166 to Day 194 after Visit 6 ^d	
Future Biomedical Research														
Blood (DNA) for Future Biomedical Research (Optional) for adult participants ≥18 years of age.		X												Collected from randomized participants who provided consent for future biomedical research (Section 8.8)
Saliva (DNA) for Future Biomedical Research for pediatric participants <18 years of age.		X												Collected from randomized participants who provided consent/assent for Future Biomedical Research (See Section 8.8).

^a When scheduling the Phone Contact (Day 15) and Visit 3 (Day 30), “Day 1” is the date of Visit 2 vaccination.
^b When scheduling the Phone Contact (Day 45) and Visit 4 (Day 60), “Day 1” is the date of Visit 3 vaccination.
^c When scheduling the Phone Contact (Day 75) and Visit 5 (Day 90), “Day 1” is the date of Visit 4 vaccination.
^d This Phone Contact (6 months after Visit 6) will only be conducted in recipients of V114 or Prevnar13™ at Visit 6.

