17. A WOCBP who has a positive urine or serum pregnancy test before the 1st vaccination at Visit 2.

Prior/Concomitant Therapy

18. Received chimeric antigen receptor T-cell (CAR-T) therapy or checkpoint inhibitor directed therapy (ie, anti PD-1) after allo-HSCT.
19. Received or planned to receive anti- CD20 B-cell targeted therapy (eg, rituximab) after allo- HSCT.
20. *Received systemic steroids at a prednisone equivalent dose >0.5 mg/kg/day (steroids at a prednisone equivalent dose \leq 0.5 mg/kg/day are allowed) for \geq 14 consecutive days and has not completed treatment at least 30 days before administration of any study vaccine.
21. *Prior or scheduled receipt of immunoglobulins or plasma products within 30 days of administration of study vaccine.
22. Non-study pneumococcal vaccine administered after allo-HSCT, or is expected to receive non-study pneumococcal vaccine during participation in the study.
23. *Received any licensed, non-live vaccine within 14 days before receipt of any study vaccine, or is scheduled to receive any licensed, non-live vaccine within 14 days after receipt of any study vaccine.
Exception: inactivated influenza vaccine and haemophilus influenzae type B (Hib) vaccine may be administered, but only if it is administered at least 7 days before receipt of any study vaccine and/or at least 7 days after receipt of any study vaccine.
24. *Received any live vaccine within 30 days before receipt of any study vaccine or is scheduled to receive any live vaccine within 30 days after receipt of any study vaccine.

Prior/Concurrent Clinical Study Experience

25. Is currently participating or has participated in an interventional clinical study with an investigational compound/agent or device within 2 weeks of participating in this current study, or plans to receive any investigational compound/agent or device (in addition to existing therapy) within 2 weeks of any vaccination, that in the opinion of the investigator would interfere with the evaluation of the study objectives.

Other Exclusions

26. Is, at the time of signing informed consent/assent, a user of recreational or illicit drugs or has had a recent history (within the last year) of drug or alcohol abuse or dependence as assessed by the study investigator.

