6.5 Concomitant Therapy

Medications or vaccinations specifically prohibited in the exclusion criteria are not allowed during the ongoing study. If there is a clinical indication for any medication or vaccination specifically prohibited, discontinuation from study intervention may be required. The investigator should discuss any questions regarding this with the Sponsor Clinical Director. The final decision on any supportive therapy or vaccination rests with the investigator and/or the participant's primary physician. However, the decision to continue the participant on study intervention requires the mutual agreement of the investigator, the Sponsor, and the participant.

Listed below are specific restrictions for concomitant therapy or vaccination:

1. Any administration of a non-study pneumococcal vaccine is prohibited during the study.
2. Administration of any non-live vaccine within the 14 days before or 14 days after receipt of any study vaccine is prohibited.
Exception: Inactivated influenza vaccine and haemophilus influenzae type B (Hib) vaccine may be administered but must be given at least 7 days before and at least 7 days after receipt of any study vaccine.
3. Administration of any live vaccine within 30 days before or 30 days after receipt of any study vaccine is prohibited.
4. Administration of immunoglobulins or plasma products is prohibited within 30 days of administration of any study vaccine.

Any deviation from the above requires consultation between the investigator and the Sponsor and written documentation of the collaborative decision on participant management.

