9.5 Analysis Populations

9.5.1 Immunogenicity Analysis Populations

The Per-Protocol (PP) population will serve as the primary population for the analysis of immunogenicity data in this study. The PP population consists of all randomized participants without deviations from the protocol that may substantially affect the results of the immunogenicity endpoints. Potential deviations that may result in the exclusion of a participant from the PP population for all immunogenicity analyses include the following:

- Failure to receive study vaccine at Visit 2 (Day 1), Visit 3 (Day 30), and Visit 4 (Day 60)
- Failure to receive correct clinical material as per randomization schedule (ie, participants who were cross-treated) at Visit 2 (Day 1), Visit 3 (Day 30), and Visit 4 (Day 60)
- Receipt of prohibited medication or prohibited vaccine prior to study vaccination at Visit 2 (Day 1), Visit 3 (Day 30), and Visit 4 (Day 60)

Additional potential deviations that may result in the exclusion of a participant from the PP population for specific immunogenicity analyses (depending on the time point) include:

- Failure to receive study vaccine at Visit 6 (Month 12 after allo-HSCT)
- Receipt of prohibited medication or prohibited vaccine prior to a blood sample collection
- Collection of blood sample outside of the pre-specified window (as described in Section 1.3)

The final determination on protocol deviations, and thereby the composition of the PP population, will be made prior to the final unblinding of the database. Participants will be included in the vaccination group to which they are randomized for the analysis of immunogenicity data using the PP population.

A supportive analysis using the Full Analysis Set (FAS) population will also be performed for the primary immunogenicity endpoints. The FAS population consists of all randomized participants who received at least 1 vaccination and have at least 1 serology result. Participants will be included in the vaccination group to which they are randomized for the analysis of immunogenicity data using the FAS population.

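### The immunoglobulin/plasma restriction ends 30 days after dose 3, but the Day 90 sample may be drawn up to 43 days after it, and the Per-Protocol rules do not list use in that gap (minor)

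*Combined protocol and SAP*

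**What the plan says.** **Restriction.** Section 6.5 item 4: "Administration of immunoglobulins or plasma products is prohibited within 30 days of administration of any study vaccine". Exclusion criterion 21 in Section 5.2 carries the same limit: "Prior or scheduled receipt of immunoglobulins or plasma products within 30 days of administration of study vaccine". Section 6.5 opens with a general carry-over rule: "Medications or vaccinations specifically prohibited in the exclusion criteria are not allowed during the ongoing study".

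**Sampling window.** The Schedule of Activities sets Visit 5, the Day 90 draw, at "Day 30 to Day 44 after Visit 4". Footnote c says that, for this visit, Day 1 "is the date of Visit 4 vaccination".

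**Analysis sets.** Section 9.5.1 builds the Per-Protocol (PP) population by removing participants with protocol deviations likely to affect immunogenicity. Among the potential time-point-specific deviations it lists "Receipt of prohibited medication or prohibited vaccine prior to a blood sample collection", and samples drawn outside the window. The supportive set is wider: "The FAS population consists of all randomized participants who received at least 1 vaccination and have at least 1 serology result".

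**Endpoint.** Section 4.2.1.1 says the sera are meant to measure IgG induced by the vaccine. Sections 9.4.1 and 9.6.1 make the within-group IgG GMC at Day 90, serotype by serotype, the primary immunogenicity result.

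**The concern.** The restriction is tied to the dose, while the endpoint is tied to the draw, and the draw may come later than the restriction reaches. The assay measures binding IgG in serum and cannot tell vaccine-induced antibody from antibody given in a blood product. If a participant first receives such a product after the restriction has lapsed and before the draw, the result is in window and no prohibited medication has been used, so the sample stays in PP.

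At stake is the level of a within-group GMC. Randomization does not correct a within-group estimate. Agreement between PP and FAS would not reveal the problem either, because both sets keep the sample.

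**Working it through.** **1. Gap before the Day 90 draw.** Inputs: window Day 30 to Day 44, Day 1 = dose 3 (Section 1.3, footnote c); restriction up to 30 days after a dose (6.5 item 4).

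- A draw on Day d falls d − 1 days after dose 3, so the window is 29 to 43 days after the dose.
- The restriction reaches +30 days, which is Day 31.
- Uncovered days = max(0, (d − 1) − 30), counting the draw day itself. Day 30: 0. Day 31: 0. Day 32: 1. Day 44: 43 − 30 = 13.
- If the window were read as elapsed days, ignoring footnote c, the maximum would be 44 − 30 = 14.

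**2. Is there a gap between doses?** Visit 3 is set at "Day 30 to Day 44 after Visit 2", and Visit 4 has the same window after Visit 3, so doses are 29 to 43 days apart. The 30 days after one dose and the 30 days before the next overlap by 60 − 43 = 17 to 60 − 29 = 31 days. Cover is unbroken from 30 days before dose 1 to 30 days after dose 3: 30 + 2 × 29 + 30 = 118 days to 30 + 2 × 43 + 30 = 146 days. Only participants with no such use in that span fall newly into the gap.

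**3. Does the restriction before Visit 6 close the gap?** Visit 6 may fall as early as day 335 after transplant, so its restriction may start on day 305. The latest dose 3 is 180 + 2 × 43 = day 266, with gap days 297 to 309. In that corner case days 305 to 309 are covered. With Visit 6 on day 365 the restriction starts on day 335 and never meets the gap.

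**4. Visit 7.** The window is again Day 30 to Day 44 after the Visit 6 dose. On the same day count the same gap of up to 13 days applies, for exploratory endpoints only.

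**5. The plan's own precision.** 150 × 0.70 = 105 evaluable per group, as stated. Table 7, SD 1.0 and GMC 1: exp(±1.96 × 1.0/√105) = (0.83, 1.21), as printed. The normal quantile reproduces all nine cells apart from one difference of 0.01 (12.11 against 12.10). The t quantile named in 9.6.1 gives (0.82, 1.21). At GMC 1 the upper limits are 1.21, 1.33 and 1.47 for SD 1.0, 1.5 and 2.0.

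**6. Size, for scale only.** The documents give no rate of use and no passive titre, so both inputs here are assumed. If m of 105 samples are raised k-fold, the GMC is multiplied by k^(m/105).

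| m | k = 2 | k = 5 |
|---|---|---|
| 1 | 2^(1/105) = 1.007 | 5^(1/105) = 1.015 |
| 3 | 2^(3/105) = 1.020 | 5^(3/105) = 1.047 |

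**7. Effect of removing samples.** If the m participants removed would have had vaccine-induced IgG f-fold below the rest, leaving them out multiplies the GMC by f^(m/105) relative to their uncontaminated values. For f = 2 to 5 and m = 1 to 3 this is again 1.007 to 1.047.

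**The case against.** **The carry-over rule.** The opening sentence of 6.5 could be read as a ban for the whole study. The narrower reading is more natural: the sentence imports what the exclusion criteria prohibit, criterion 21 has its own 30-day limit, and a whole-study ban would leave item 4 without purpose. The text is not unequivocal, however.

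**The PP list is open.** Section 9.5.1 gives potential deviations, does not claim to be exhaustive, is settled before unblinding, and has an item tied to the blood sample. A reader might infer that reviewers would have no pointer to this case. That goes too far, because the item does direct attention to the period before each draw. But PP exclusion still requires a deviation, and permitted use is not one.

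**Materiality.** The study is descriptive, with no hypothesis tests, and the assumed effects are far smaller than the sampling error. This stands and sets the grade. A reader might also take 13 of 15 permitted draw days as wide exposure. Those are calendar days, not samples, and a draw on Day 30 has no gap.

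**Data source.** One might suppose that the data needed are certainly collected already. The documents do not settle this. The schedule marks a medication review at Visits 5 and 7, and the first sentence of 8.1.5.2 covers medication during the study. But the next paragraph of 8.1.5.2 sends recording to the electronic report card, which 8.3.4 limits to Days 1 to 14 after vaccination. The gap lies after that.

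**Selection.** Removing samples for a post-randomization event can itself move the GMC. This stands, and is why both results should be shown.

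**Conclusion.** The point holds as a minor one. The dose-based restriction and the draw window do not match. For draws on Day 32 to Day 44 there are 1 to 13 days in which first use is generally not prohibited (except where an early Visit 6 brings its own restriction forward), is not a listed PP deviation, and leaves the sample in both PP and FAS.

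A reader might infer that the primary GMCs are materially inflated or that the vaccine comparison is biased. The documents support neither. They give no number of users and no passive titre, and allocation is randomized and blinded, so no difference between groups is expected from this source. The factor of 1.007 to 1.047 rests on assumed inputs (1 to 3 of 105 samples, each raised 2- to 5-fold), against Table 7 upper limits of 1.21 to 1.47 times the GMC. The conclusion also assumes footnote c's day count, the narrower reading of 6.5, and that the products carry pneumococcal antibody.

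**What to change.** Analysis only; no change to clinical management is proposed.

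- In 9.5.1, or in the supplemental SAP before unblinding, add a time-point-specific PP criterion: receipt of any immunoglobulin or plasma product between dose 3 and the Day 90 draw, or between the Visit 6 dose and the Visit 7 draw, whether or not prohibited. Exclude only the affected sample.
- Report the number of such samples per group, and show the GMC with and without them.
- Name the medication review at Visits 5 and 7 (Schedule of Activities; 8.1.5.2, first sentence) as the data source, and confirm that it captures use after Day 14.

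Cost: one line of text, one extra display and one check of the data source. If the review captures later use, no new collection is needed; if it does not, the criterion cannot be applied reliably and the report should say so. A few samples would leave PP, with little loss of precision: with 3 removed (n = 102, SD 1.0, GMC 1) the t-based interval is (0.82, 1.22), against (0.82, 1.21) at 105.

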6.5.1 Rescue Medications and Supportive Care

No rescue or supportive medications are specified to be used in this study.

6.6 Dose Modification (Escalation/Titration/Other)

No dose modification is allowed in this study.

6.7 Intervention After the End of the Study

There is no study-specified intervention following the end of the study.

6.8 Clinical Supplies Disclosure

This study is blinded but supplies are provided open label; therefore, an unblinded pharmacist or qualified study site personnel will be used to blind supplies. Study intervention

identity (name, strength, or potency) is included in the label text; random code/disclosure envelopes or lists are not provided.

The emergency unblinding call center will use the intervention/randomization schedule for the study to unblind participants and to unmask study intervention identity. The emergency unblinding call center should only be used in cases of emergency (see Section 8.1.12). In the event that the emergency unblinding call center is not available for a given site in this study, the central electronic intervention allocation/randomization system (IRT) should be used to unblind participants and to unmask study intervention identity. The Sponsor will not provide random code/disclosure envelopes or lists with the clinical supplies.

See Section 8.1.12 for a description of the method of unblinding a participant during the study, should such action be warranted.

7 DISCONTINUATION OF STUDY INTERVENTION AND PARTICIPANT WITHDRAWAL

7.1 Discontinuation of Study Intervention

Discontinuation of study intervention does not represent withdrawal from the study.

As certain data on clinical events beyond study intervention discontinuation may be important to the study, they must be collected through the participant's last scheduled follow-up, even if the participant has discontinued study intervention. Therefore, all participants who discontinue study intervention prior to completion of the protocol-specified vaccinations will still continue to participate in the study as specified in Section 1.3 and Section 8.12.3, unless the participant withdraws consent (Section 7.2).

Participants may discontinue study intervention at any time for any reason or be discontinued from the study intervention at the discretion of the investigator should any untoward effect occur. In addition, a participant may be discontinued from study intervention by the investigator or the Sponsor if study intervention is inappropriate, the study plan is violated, or for administrative and/or other safety reasons. Specific details regarding procedures to be performed at study intervention discontinuation are provided in Section 8.1.11.

A participant must be discontinued from study intervention but continue to be monitored in the study for any of the following reasons:

- The participant requests to discontinue study intervention.
- The participant has a medical condition or personal circumstance which, in the opinion of the investigator and/or Sponsor, placed the participant at unnecessary risk from continued administration of study intervention.
- The participant has a confirmed positive urine or serum pregnancy test before any study vaccination visit.

For participants who are discontinued from study intervention but continue to be monitored in the study, see Section 1.3 and Section 8.12.3 for those procedures to be completed at each specified visit.

Discontinuation from study intervention is “permanent.” Once a participant is discontinued, he/she shall not be allowed to restart study intervention.

